### 3.0 STUDY DESIGN/METHODOLOGY

**Aim I: Primary Care and Community-based Organizations:** Conduct a baseline assessment of how primary care practices, public health programs, and community-based organizations are initially addressing initiation and completion of the HPV vaccine series.

We have already determined HPV vaccination rates in 53 rural primary care practices (available from the Oregon Immunization Program – OIP), which has helped us identify “hot spots” for intervention research. We will conduct a baseline assessment in 20 of these practices using direct observation of workflows and validated measures of team-based care effectiveness and practice-level knowledge of HPV and current HPV vaccine recommendations. This will assist us in developing tailored intervention approaches for busy rural primary care practices and enable us to assess which practice characteristics affect delivery of the full HPV series. We will also conduct an in-depth assessment of activities undertaken in rural Oregon communities to inform the public about cancer risks and HPV vaccines.

**Aim II: Primary Care:** Implement and test, using a stepped-wedge cluster randomized trial design, the effectiveness of a multi-component primary care practice-based intervention on initiation of and completion of the HPV vaccine series as well as reduction in rates of missed opportunities to vaccinate.

The intervention will be conducted in 40 primary care practices we plan to enroll and will involve: 1) practice facilitation to engage clinics in a practice-wide planning process to redesign patient care and communication strategies to optimize HPV vaccine completion; 2) workflow mapping adapted to practice context to support HPV vaccine delivery; 3) a practice improvement model designed to firmly establish reminder and recall systems and standing orders; and 4) education for patients and parents that underscores HPV vaccination is safe, effective, and an important approach for reducing cancer risk. We will additionally explore uptake of the intervention in terms of implementation timing and component features in high- and low-functioning practices to determine which practice characteristics affect delivery of the full HPV series.

**Aim III: Community Organizations:** To explore the extent to which an evidence-based social marketing campaign, implemented in partnership with participating practices, will increase HPV vaccine demand.

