Aims II and III: Members in each practice (n=40) will be asked to complete a Practice Survey (PS) at baseline and again annually (for variables that might change). The PS ascertains information about practice and practice’s patient demographics, practice change, payer mix, revenue and payments, HPV vaccine priority, internal structure and strategies for improving HPV vaccine rates, external reporting, registries, and clinical guideline availability. A Staff Member Survey (SMS) will also be administered at baseline and annually (for variables that might change). It ascertains information on staff member demographics, adaptive reserve, patient needs, clinician and staff satisfaction and burnout, staff motivation, staff turnover, practice leadership, practice cohesion and rewards, and practice readiness to change. A Quality Improvement Change Assessment (QICA) will be administered every six months. It ascertains information on the foundational change concepts for building quality improvement (QI) capacity in primary care: Organized, Evidence-Based Care; Quality Improvement Strategy; Continuous & Team-Based Healing Relationships; and Care Coordination. Intervention Site Visits will be conducted monthly, which will involve workflow mapping; patient data collection: eligible patient population, patient demographics, and other characteristics of the patient population; quarterly immunization rates; quarterly community education data collection: existing education programs, efforts, and partnerships; PDSA cycle worksheets; and field notes. We will also conduct Patient/Parent Surveys every six months, which will ascertain children’s and parents’ knowledge about cancer risk reduction and the HPV vaccine series, where and how information about HPV and cancer risk reduction via vaccination was sought, and patient and parental demographic information. Lastly, we will conduct Pre- and Post-Community Partner surveys and Group Interviews that will assess perspectives on community acceptability of HPV vaccination.

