## 13.0 BIO-STATISTICAL CONSIDERATIONS

Our proposed stepped-wedge cluster randomized trial (78) will evaluate the impact of the proposed intervention on HPV outcomes in 40 primary care practices (Aim II). We will specifically test two hypotheses: 2a) More patients will have initiated and completed the HPV vaccine series in intervention practices compared to control practices, and 2b) Practices receiving the intervention will have lower rates of missed opportunities to vaccinate compared to control practices. The primary outcome variables will include receipt rate of the initial (age 11-12 years) and full series of HPV vaccines and a reduction in the rates of missed opportunities to vaccinate among males and females aged 11-17 years. We will conduct block randomization of practices in five waves every six months. Outcomes will be measured every three months in all clusters at every period, so that each cluster provides data points in both the control and intervention conditions. Practices in each wave will be stratified based on designation of pediatric or family medicine clinic to balance pediatric/family medicine clinics at each wave. Outcome data collection will be collected from ALERT IIS beginning in quarter four of the study and up to 17, for 14 longitudinal data collection points per practice. [name], who has no contact with the study practices, will perform the randomization for all practices prior to the start of the first intervention wave. Randomized assignment will not be revealed to practices until their cluster begins the study.

The primary goal of Aim II is to establish whether the intervention is effective and the degree to which it is accomplishing its goals. Our outcome evaluation includes a rigorous research design so we may attribute positive findings to the intervention and not to existing threats to internal validity. To compare the effect of the intervention with usual care on HPV outcome measures in the context of a stepped-wedge design, we will utilize Generalized Linear Mixed Models (GLMMs) (79). In particular, to assess the intervention effect, we will use a Poisson model with random effects for practice. The general model is as follows:

$$(1) \log(Y_{it}|b_i) = \beta_0 + \beta_1 t + \beta_2 I_{it} + \beta_3 I_{it}(t - s_i) + \beta_4 Z_i + b_i + \log(E_{it})$$

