where  $Y_{it}$  is the number of patients in practice  $i$  who had HPV completion during period  $t$  for  $t \in (0, 1, \dots, 13)$ . Data is collected every three months (i.e., quarterly), and  $t = 0$  is the baseline quarter. Additionally,  $I_{it}$  is an indicator variable where  $I_{it} = 1$  if practice  $i$  has been assigned to the intervention at period  $t$ , and  $I_{it} = 0$  otherwise. Term  $s_i$  is the period when the intervention begins for practice  $i$ . The practice-level term to denote a family medicine or pediatric practice is denoted by  $Z_i$  where  $Z_i = 1$  if practice  $i$  is a family medicine practice and  $Z_i = 0$  if pediatric practice.  $E_{it}$  is the number of patients in the practice  $i$  who were eligible to be counted during period  $t$  and the  $\log(E_{it})$  term is considered the 'offset' in the Poisson regression model. The term  $b_i$  denotes a random effect term for practice  $i$  with mean 0 and variance  $\sigma_b^2$ . The estimation via model (1) takes into account the general time trend, and allows for the intervention effect to grow over time following intervention implementation. Model (1) estimates the intervention effect with the within site difference between HPV completion rates pre- and post-intervention, averaging across practices and accounting for possible secular trends which might confound with the timing of the intervention implementation. In model (1),  $\beta_0$  is the (log of) average pre-intervention HPV completion rate for pediatric practices (i.e.,  $Z_i = 0$ ) with the random effect set to 0.  $\beta_1$  is the effect of the general time trend of the HPV completion rate without the intervention.  $\beta_2$  represents the intervention effect that appears in the first time period of the intervention.  $\beta_3$  represents the added intervention effect that accrues over time following intervention implementation. Model (1) will also apply for outcome of HPV initiation, completion, and rates of missed opportunities to vaccinate by replacing  $Y_{it}$  and  $E_{it}$  with the appropriate numerator and denominator. Hypothesis tests will be two-sided, with type I error set to 0.05. Because statistical tests are specified a priori and our proposed outcome measures are highly related, we will follow recommendations to report p-values rather than adjust for multiple comparisons (80, 81). Goodness of fit statistics and model fitting diagnostics will be used to assess for influential points and over-dispersion and to evaluate alternative model specifications.

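### Model (1) gives every practice the same intervention effect although the intervention is tailored, so the reported interval is too narrow if practices respond differently

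*Combined protocol and SAP*

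**What the plan says.** Section 13.0 of the combined protocol and SAP bases the outcome analysis on model (1): "we will use a Poisson model with random effects for practice". The only random quantity is b_i, which "denotes a random effect term for practice" with mean 0 and a single variance.

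The intervention enters through two fixed coefficients without a practice index. β2 "represents the intervention effect that appears in the first time period of the intervention", and β3 is the further effect gained per quarter. The one practice covariate is Z_i ("The practice-level term to denote a family medicine or pediatric practice is denoted by" Z_i), entered as a main effect and not crossed with the intervention indicator I_it.

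The intervention itself differs between practices. Section 3.0 lists "workflow mapping adapted to practice context to support HPV vaccine delivery" among its components, and section 1.0 argues that a tailored approach is needed because barriers do not carry over from one setting to another. Section 3.0 also plans an exploratory look at uptake "in high- and low-functioning practices to determine which practice characteristics affect delivery of the full HPV series".

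Section 13.0 provides for diagnostics of influential points and over-dispersion, and for considering other model specifications, without naming any.

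**The concern.** A random intercept lets practices differ in their vaccination level, not in how much the intervention changes it. If the change varies, all the intervention quarters of one practice share a deviation that model (1) leaves out of its covariance. The model then treats those quarters as more independent evidence about the effect than they are, and its standard error for β2 and β3 is too small.

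At stake is the interval around the main Aim II result. The plan describes an intervention fitted to each practice and expects practice characteristics to matter, so a common effect is an assumption that its own rationale makes doubtful.

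**Working it through.** **Inputs from section 13.0.** 40 practices in five cohorts of eight, starting two quarters apart; 14 quarters (t = 0 to 13); baseline completion 24%; ICC 0.08; the power contrast is the sixth quarter after the start.

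**Inputs assumed, because the documents do not give them.**
- Start quarters t = 1, 3, 5, 7, 9, and equal practice sizes.
- m eligible patients per practice-quarter: 5, 40 or 100.
- SD of practice-specific log rate ratios, τ: 0.1, 0.2 or 0.3.
- Practice-intercept SD 0.5 on the log scale. ICC 0.08 gives about this value: √(0.08 × 0.24 × 0.76)/0.24 = 0.50.

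**Step 1: the plan's own figure.** The detectable change from 24.0% to 43.4% is ln(43.4/24.0) = 0.592 on the log scale. With 80% power at two-sided 0.05, the implied SE is 0.592/(1.960 + 0.842) = 0.211. The stated figure cannot be reproduced directly, since m and the start quarters are missing. Solving model (1) backwards for an SE of 0.211 gives m of about 5. That is why m = 5 is in the range.

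**Step 2: the SE that model (1) reports.** For each practice, let X hold the columns 1, t, I_it and I_it(t − s_i). Take V0 = [1/(0.24m)]·Id + 0.25·J, where Id is the identity matrix, J is a matrix of ones and 0.25 = 0.5². The contrast is c = β2 + 5β3, the sixth intervention quarter. The reported variance is c′A⁻¹c, with A = ΣX′V0⁻¹X.

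**Step 3: the actual SE of the same estimator when effects vary.** The true covariance is V = V0 + τ²·II′, where I is the practice's vector of intervention indicators. The actual variance is c′A⁻¹BA⁻¹c, with B = ΣX′V0⁻¹VV0⁻¹X. With r = actual SE/reported SE, coverage is 2Φ(1.96/r) − 1.

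| m | τ | reported SE | actual SE | ratio | coverage |
|---|---|---|---|---|---|
| 5 | 0.1 | 0.2035 | 0.2052 | 1.008 | 95% |
| 5 | 0.2 | 0.2035 | 0.2100 | 1.032 | 94% |
| 5 | 0.3 | 0.2035 | 0.2178 | 1.070 | 93% |
| 40 | 0.1 | 0.0888 | 0.0915 | 1.030 | 94% |
| 40 | 0.2 | 0.0888 | 0.0990 | 1.115 | 92% |
| 40 | 0.3 | 0.0888 | 0.1104 | 1.244 | 88% |
| 100 | 0.1 | 0.0578 | 0.0617 | 1.068 | 93% |
| 100 | 0.2 | 0.0578 | 0.0722 | 1.249 | 88% |
| 100 | 0.3 | 0.0578 | 0.0869 | 1.503 | 81% |

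Ratios use unrounded SEs.

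**Step 4: checks.**
- A Poisson simulation at τ = 0.2 and m = 100 gave 84.9% coverage for this contrast, somewhat below the formula's 88%. With no variation in effect it gave 94–95%, so the loss comes from the omitted term.
- For the first-quarter effect β2 alone, the ratios at m = 100 are larger: 1.12, 1.41 and 1.79.
- If the true cell variance is binomial, 0.76/(0.24m), while the Poisson model is still fitted, the ratios at τ = 0.1, 0.2 and 0.3 fall to 0.92, 1.01 and 1.15 (m = 40) and 0.95, 1.15 and 1.42 (m = 100).

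**Scale of τ.** If the mean effect equals the planned 0.592 (rate ratio 1.81), then exp(0.592 ± 1.96τ) gives the range holding about 95% of practices' rate ratios: 1.49–2.20 at τ = 0.1, 1.22–2.68 at 0.2 and 1.00–3.25 at 0.3.

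**The case against.** The strongest reply is that the size rests on inputs the plan does not contain. At the practice-quarter size that its own power statement implies, the understatement is at most 7% over this range. Under binomial variation the Poisson model's surplus variance absorbs it there altogether. This stands. It is why the finding is a range whose lower end is negligible.

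It is also true that if the intervention works nowhere, there is no variation in effect, and the test of that null is not inflated. The problem concerns the interval around a real average effect.

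The diagnostics in section 13.0 are partial mitigation. Variation in effect can show up as over-dispersion. But the section names no random intervention effect, no robust variance and no trigger, so what would follow is left open.

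Four stronger readings are tempting, and the documents do not support them:
- *The question on high- and low-functioning practices cannot be answered.* Section 3.0 frames it as exploratory and around uptake and implementation timing. Section 13.0 gives overall effectiveness as the primary goal of Aim II and does not offer model (1) as the analysis of functioning. The practice data are collected, so model (1) could be extended. What is missing is a definition and a prespecified analysis.
- *Practices will be grouped by scores affected by the intervention.* Section 8.0 says "A Quality Improvement Change Assessment (QICA) will be administered every six months", but no passage makes it the measure of functioning or proposes grouping by scores taken after crossover.
- *The text promises equal weight per practice.* The phrase "averaging across practices and accounting for possible secular trends" does not say so, and a patient-weighted effect is a legitimate target.
- *Table 1 gives the quarterly denominator.* Its 21,574 over 40 practices is about 539 each, but that is total planned enrolment at ages 11–17. Section 8.0 measures initiation at 11–12 and completion at 13–17. No ratio here uses it.

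**Conclusion.** The concern holds in this form: model (1) assumes one intervention effect for all practices, the intervention is designed to differ between them, and any variation in effect makes the model-based interval too narrow. Under Poisson variation the SE understatement for the sixth-quarter effect runs from about 1% (5 eligible, SD 0.1) to 50% (100 eligible, SD 0.3), with coverage from 95% down to 81%. It is smaller under binomial variation.

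The result rests on the assumed SD of effects, eligible count, start quarters and equal practice sizes. Moving the starts one quarter later raises the ratios slightly, for example from 1.25 to 1.29 at m = 100 and SD 0.2. The direction follows from the model; the size has to come from the trial's own data. The change is worth making because it is cheap and touches the main analysis.

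**What to change.** In section 13.0, add a practice-level random intervention effect, b_1i·I_it, to model (1), and a random slope on I_it(t − s_i) if it can be estimated. Report the estimated SDs with the average effect. Alternatively, keep the common coefficients and use a variance estimate clustered on practice, with a small-sample correction suited to 40 practices. State in advance which is primary, and name the other as the fallback if the random-effects model does not converge.

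The cost is one or two model terms, no new data, a wider interval when effects vary, and possible convergence problems. There is some gain too: at m = 100 and SD 0.3, fitting the correct covariance gives an actual SE of 0.0769 against 0.0869 for the common-effect estimator.

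Secondary and exploratory: if the effect is compared between high- and low-functioning practices, define functioning in advance and test its interaction with I_it. Use a measure taken before that practice's own crossover, for example the baseline Staff Member Survey or Practice Survey, or a QICA score from before crossover. Say that precision will be low. A 20/20 split doubles the SE, so a design with exactly 80% power for 0.592 has power Φ(0.592/(2 × 0.211) − 1.96) ≈ 29% for a difference as large as the whole planned effect.

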## 1.0 BACKGROUND/ RATIONALE

Dangers Associated with the Human Papilloma Virus & Vaccine Recommendations: HPV-16 and -18 account for about 70% of cancers of the cervix, vagina, and anus and for approximately 30-40% of cancers of the vulva, penis, and oropharynx (4). Other cancers linked to HPV include non-melanoma skin cancer and cancer of the conjunctiva (3). About \$8 billion is spent annually to manage the sequelae of HPV infections, primarily to manage abnormal cervical cytology and cervical neoplasia (1). This exceeds the economic burden of any other sexually transmitted infection except for the human immunodeficiency virus (1).

In 2006, the Food and Drug Administration approved a vaccine to protect against strains of the virus (5), including HPV-16 and -18. Currently, three vaccines (Cervarix, Gardasil, and Gardasil 9) are available (13), and vaccination is recommended starting at age 11 or 12 years for **both males and females**. Unfortunately, the U.S. National Immunization Survey (NIS) has shown that completion of the vaccine series (three shots) often does not occur despite recommendations by several groups (6, 13, 14). Regarding females, national vaccine initiation among 13-17 year olds increased from 53% in 2011 to 60% in 2014. However, vaccine series completion was only 39.7% nationally, with regional variation by state (20.1%-56.9%) (6). Regarding males, modest increases occurred between 2014 to 2015 for initiating the HPV vaccine series (from 41.7% to 49.8%), with completion of the series increasing only from 21.6% to 28.1% (7). In late 2016, the Advisory Committee on Immunization Practices (ACIP) has approved a schedule change for HPV vaccination completion. The ACIP recommends the use of a 2-dose schedule for girls and boys who initiate the vaccination series at ages 9 through 14 years. Three doses remain recommended for persons who initiate the vaccination series at age 15 through 26 years and for immunocompromised persons (15). This policy change will be taken into account in our analyses. HPV vaccination coverage remains lower than meningococcal ACWY (MCV) and tetanus, diphtheria, and acellular pertussis (Tdap) vaccine rates (16). This gap points to the opportunity to reduce missed opportunities for HPV vaccinations.

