
**Power Calculations:** We assess the power to detect effects that are clinically meaningful and realistic. For this calculation, we assess the power to detect at least 80% power of a 2-sided significance test with  $\alpha = 0.05$ . We are interested in comparing the rate of HPV completion in the sixth quarter after intervention with HPV completion rate at baseline. Given the following conditions: 1) Pre-specified total sample size of 40 practices; 2) Design (stepped-wedge with five cohorts of eight practices starting six months apart); 3) Two-sided significance level of 0.05; 4) Starting practice-level HPV completion of 24% as described above; 5) Intra-cluster correlation (ICC) of patients within practices of 0.08 (82, 83), we will have at least 80% power to detect a minimum of 19.4% difference in the absolute change (increasing from 24.0% to 43.4%). If we are successful at retaining all 45 practices that will be recruited, we will have at least 80% power to detect a 18.1% difference in absolute change. These estimates assume a conservative ICC of 0.08. As most studies show an  $ICC < 0.001$  (84), the proposed study will have sufficient power to detect differences of health policy importance. Estimates of parameters for these power

calculations were obtained from model (1) and the most recent, up-to-date OIP dataset. These power calculations estimate the minimum numbers needed to detect minimum changes.

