Analysis Considerations: If we find significant practice differences between cohorts, we will utilize propensity score weighting methods to reduce the observed bias, help minimize external threats to the validity of results, and adjust for imbalances (85, 86). Additionally, model (1) can accommodate missing data resulting from practice attrition. We will explore model missingness by including relevant variables in the analysis as covariates (87, 88). If non-trivial levels of missing data are observed, we will use methods such as multiple imputation to include these practices in analyses (87). We will conduct a sensitivity analysis comparing parameter values for models using completers only, all practices without multiple imputation, and all practices with multiple imputation, to understand any biases introduced by differential attrition or missing not at random (88). Our project has control, intervention, and follow-up periods in all seasons, which will allow us to detect and account for the potential effect of seasonality on the receipt of indicated adolescent vaccines.

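### Model (1) gives calendar time a single log-linear slope and no season term, so a curved or seasonal common trend biases the intervention effect; quarter effects should be prespecified

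*Combined protocol and SAP*

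**What the plan says.** Model (1) in section 13.0 is a Poisson mixed model for 40 practices over quarters t = 0 to 13. Its terms are an intercept, β1·t, an immediate intervention effect β2, a linear growth in that effect β3, practice type, a practice random effect and an offset. The text says of β1 that it "is the effect of the general time trend of the HPV completion rate without the intervention", and of the model that it "takes into account the general time trend, and allows for the intervention effect to grow over time following intervention implementation". It presents the resulting estimate as "accounting for possible secular trends which might confound with the timing of the intervention implementation".

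Three other statements bear on the point:

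- **Season.** The Analysis Considerations paragraph says control, intervention and follow-up periods fall in all seasons, "which will allow us to detect and account for the potential effect of seasonality on the receipt of indicated adolescent vaccines". No season term is given.
- **Other model forms.** Diagnostics will be used "to assess for influential points and over-dispersion and to evaluate alternative model specifications". No form, trigger or replacement rule is named.
- **Dose-schedule change.** Section 1.0 says the late-2016 change will be dealt with in the analyses. Model (1) has no term for it.

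The design has five waves at six-month intervals ("We will conduct block randomization of practices in five waves every six months"). Power is stated for "comparing the rate of HPV completion in the sixth quarter after intervention with HPV completion rate at baseline".

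**The concern.** In a stepped-wedge trial, intervention exposure rises with calendar time by construction, so the effect estimate depends on how time is modelled. A single slope removes a common trend only if that trend is straight on the log scale. Whatever it misses is shared among β2, β3 and the residual.

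Staggered starts give concurrent controls during rollout, so only part of any misfit reaches β2 and β3. Once the last wave has started, no practice is in control. From there on, separating trend from effect leans on the assumed slope. The powered contrast lies five quarters after the start quarter, so any error in β3 enters it five times over.

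At stake are the size and p-value of the main effect: benefit understated under a flattening trend, overstated under an accelerating one, and pushed either way by season.

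**Working it through.** **Inputs from the documents (section 13.0 unless noted).** 40 practices in five waves of eight; one step every two quarters; t = 0 to 13; two-sided α = 0.05; planned change 24.0% to 43.4%. Table 1 in section 4.0 gives 21,574 patients.

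**Assumptions.**
- Patients per practice-quarter: m = 539 (21,574/40), with m = 100 as a low alternative. The power section gives no cluster size.
- Wave starts at t = 1, 3, 5, 7, 9 (called 1–9), or one or two quarters later (2–10, 3–11). The overall timeline figure is not in the text available.
- Trend shapes as listed below.

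**The plan's own effect.** 43.4 − 24.0 = 19.4 points; 43.4/24.0 = 1.81 as a rate ratio. The 19.4-point detectable difference cannot be re-derived, because no cluster size or variance component is stated. Nothing below depends on it.

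**Quarters with no control practice.** Last start at t = 9: 13 − 9 + 1 = 5 of 14. Last start at t = 11: 13 − 11 + 1 = 3 of 14.

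**Why an ordinary trend is not log-linear.** Section 1.0 reports national male coverage "with completion of the series increasing only from 21.6% to 28.1"%, a one-year rise of 6.5 points. At a steady 6.5 points a year from 24%, coverage at t = 13 is 24 + 6.5 × 13/4 = 45.1%. The relative slope falls from 6.5/24 = 27% a year to 6.5/45.1 = 14% a year. A straight line in points is therefore a concave curve in logs.

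**Method.** Set the true effect to zero and give all practices the same trend. Fit model (1) to the expected counts by Poisson regression with practice effects. Counting the start quarter as the first, the sixth-quarter contrast is β2 + 5β3. Its bias is exp(β2 + 5β3), which should be 1. The rejection probability uses the model's Poisson standard error.

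**Reading A: Y/E is coverage, starting at 24%** (ranges over starts 1–9 to 3–11)

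| Common trend | Spurious ratio | Rejection, m = 539 | Rejection, m = 100 |
|---|---|---|---|
| Log-linear | 1.00 | 5% | 5% |
| +3 points/year | 0.99 | 7–9% | 5–6% |
| +6.5 points/year | 0.96–0.97 | 28–53% | 9–14% |
| Flattening to 35% (time constant 5 quarters) | 0.92 | 93–99.8% | 31–55% |
| Accelerating, 24% + 12%·(t/13)² | 1.06–1.07 | 60–91% | 16–29% |

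Rejections in rows with a ratio below 1 point towards harm. Only the accelerating trend produces false claims of benefit.

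**Reading B: Y is new completions per quarter (4% assumed), with a ±20% yearly cycle**

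| Starts | Spurious ratio, by season phase | Rejection, m = 539 | Rejection, m = 100 |
|---|---|---|---|
| 1–9 | 0.94–1.06 | 9–16% | 6–7% |
| 3–11 | 0.91–1.09 | 12–46% | 6–13% |

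With finer season phases, starts 1–9 give 0.93–1.07 and up to 21% at m = 539. Readings A and B are alternatives; their figures do not apply together.

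**Second check.** A simulation (300 runs per scenario) used a quadratic trend with a total log-rate rise of 0.5, or a season of +0.3 log rate in one quarter of each year. With a companion projection, it gave sixth-quarter ratios of 0.91–0.93 (concave), 1.07–1.10 (convex) and 0.91–1.10 (season). With quarter indicators the leak was exactly zero, and simulated rejection was 0.02–0.08.

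**After the fix.** Under every trend in Reading A, quarter effects give a ratio of 1.00 and 5% rejection. Adding only t² is not enough. It moves the flattening case (starts 1–9, m = 539) from 0.924 and 93% to 0.989 and 7%, but with starts 2–10 the ±20% season still gives 0.96–1.04 and up to 10%.

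**Precision cost.** Standard error of β2 + 5β3 at m = 539 under a log-linear trend:

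| Starts | Linear slope | Quarter effects | Rise |
|---|---|---|---|
| 1–9 | 0.0246 | 0.0261 | 6% |
| 2–10 | 0.0214 | 0.0230 | 8% |
| 3–11 | 0.0191 | 0.0211 | 10–11% |

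**The case against.** The plan is not silent. It commits to handling seasonality, foresees diagnostics and other specifications, and observes every practice in both conditions. The gap is therefore narrow: the time term, and the rule for changing it, are not prespecified. That gap stands. Section 13.0 justifies unadjusted p-values partly by saying the tests are fixed in advance, which sits badly with a time form chosen after diagnostics.

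The rejection rates deserve caution. They assume no over-dispersion. With an assumed variance inflation of 3, the flattening case falls to 50–80% (m = 539) or 14–23% (m = 100), and the accelerating case to 25–47% or 9–13%. Table 1 is a census-based planned total and need not equal the number eligible in any one quarter. The +6.5-point trend is an extreme illustration: it would carry untreated practices to 45.1%, past the design target, while the +3-point trend does almost no harm. All of this stands, but it affects the rejection rates and the choice of scenario, not the bias under a given trend shape.

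The remedy also has limits. It removes only trends common to all practices, and β3 stays linear. If the true effect ramps up and then levels off (assumed ratio about 1.75–1.8 at the sixth quarter), the quarter-effect model recovers 0.97–0.99 of it. It was still closer than model (1) in every such case tried.

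**Conclusion.** The concern holds. As written, the primary model does not deliver the protection against secular trend that section 13.0 claims for it, and no term delivers the promised handling of season. For the shapes tabulated, the bias in the sixth-quarter ratio runs from about 0.91 to 1.09. It is zero if the common trend is log-linear and about 1% for a mild steady rise.

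Against a planned ratio of 1.81 this would not overturn a result of the planned size. It could decide the p-value, and distort the estimate, for a smaller effect. The sign and size depend on trend shape, season phase, start quarters and the reading of the outcome; the rejection rates depend also on practice size and over-dispersion. The structural gap depends on none of these. It should be fixed before the outcome data are analysed.

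**What to change.** In the primary model, replace β1·t with fixed effects for the 13 post-baseline quarters:

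log(Y_it | b_i) = β0 + Σ(q = 1..13) γ_q·1(t = q) + β2·I_it + β3·I_it·(t − s_i) + β4·Z_i + b_i + log(E_it)

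These terms absorb any trend, seasonal pattern or policy shift common to all practices. State that this is the primary specification for each outcome to which model (1) applies, and keep the linear-slope model as a named sensitivity analysis.

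The change is to SAP wording and needs no new data. If the trend is in fact log-linear, the standard error of the sixth-quarter contrast rises by about 6–11%, and that of β3 alone by about 13–17%. A separate effect for each exposure quarter would also relax the linear growth, but raises the contrast's standard error by about 22%, 29% or 42% in total (starts 1–9, 2–10, 3–11). It is better left as an optional sensitivity analysis.
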